# **Evaluation of the Effect of Three Types of Rapid Maxillary Expanders (Conventional, Hybrid and MSE)**

**NCT05446714**

**Date of the document:14/5/2024**

### **Statistical analysis**

Data management and statistical analysis were performed using the Statistical Package for Social Sciences (SPSS) version 20. Data were explored for normality by checking the data distribution and using Kolmogorov-Smirnov and Shapiro-Wilk tests. Comparisons of normally distributed numeric variables between groups was performed by ANOVA test followed by Bonferroni post hoc test whenever a significance difference was detected. Pre and post values was compared by paired t test.

The mean difference was calculated by the formula:(Value after-value before)

Difference data were non-parametric and were compared between groups using Kruskal Wallis test.

All p-values are two-sided. P-values  $\leq 0.05$  were considered significant.

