- **Nasal floor molar:** There was no significant difference between groups in pre values ( $p= 0.058$ ) and post value ( $p=0.397$ ). There was a statistically significant difference between groups regarding the amount of change (difference) by treatment ( $p=0.000$ ), with the highest value recorded in MSE ( $4.38\pm0.85$ ), followed by Hybrid hyrax ( $2.6\pm1.04$ ) and the lowest value recorded in Butterfly hyrax ( $2.2\pm 1.49$ ), (Table 2, Fig.4, 13).
- **Nasal floor premolar:** There was no significant difference between groups in pre values ( $p= 0.701$ ). Regarding post treatment value, there was a statistically significant difference between groups ( $p=0.001$ ), with the highest value recorded in MSE ( $39.73\pm2.27$ ), followed by Hybrid hyrax ( $38.63\pm1.77$ ) and the lowest value

recorded in Butterfly hyrax ( $37.04 \pm 1.17$ ). Moreover, regarding the amount of change (difference) by there was a statistically significant difference between groups ( $p=0.000$ ), with the highest value recorded in MSE ( $4.87 \pm 0.62$ ), followed by Hybrid hyrax ( $3.43 \pm 0.74$ ) and the lowest value recorded in Butterfly hyrax ( $2.47 \pm 1.02$ ), (Table 2, Fig.4, 13).

- **Hard palate maxillary width 6:** There was no significant difference between groups in pre values ( $p= 0.083$ ). Regarding post treatment, the mean value recorded in MSE ( $64.31 \pm 1.8$ ) was not significantly different from butterfly Hyrax ( $63.59 \pm 2.15$ ), but was significantly higher than that recorded in Hybrid hyrax ( $62.04 \pm 2.68$ ), ( $p= .023$ ). The mean value of amount of change (difference) recorded in MSE ( $5.91 \pm 0.92$ ) was significantly higher than that recorded in Butterfly hydrax ( $3.37 \pm 0.96$ ) and Hybrid hyrax ( $3.17 \pm 1.54$ ), ( $p= .000$ ). (Table 2, Fig. 5, 14).
- **Hard palate maxillary width 4:** There was no significant difference between groups in pre values ( $p= 0.677$ ). Regarding post treatment, the mean value recorded in MSE ( $40.34 \pm 1.56$ ) was significantly higher than that recorded in butterfly hyrax ( $38.17 \pm 1.76$ ), ( $p= .002$ ). The mean value of amount of change (difference) recorded in MSE ( $6.35 \pm 1.25$ ) was significantly higher than that recorded in Butterfly hydrax ( $4.51 \pm 1.28$ ) and Hybrid hyrax ( $5.09 \pm 1.16$ ), ( $p= .001$ ). (Table 2, Fig. 5, 14).

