- **Posterior suture opening:** All groups recorded a value ( $0\pm0.00$ ) pre-treatment. Post treatment, The mean value recorded in MSE was significantly higher than that recorded in Butterfly hydrax, while Hybrid hyrax recorded a significantly lower value than the other 2 groups ( $p= .000$ ). The mean value of amount of change (increase) recorded in MSE was significantly higher than that recorded in Butterfly hydrax; while Hybrid hyrax recorded a significantly lower value than the other 2 groups ( $p= .000$ ), (Table 3, Fig 10, 18)

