Right.1 st premolar inclination	Butterfly hyrax	6.70	2.51	11.72 a	3.96	5.02 a	2.18	5.90	.000*
	Hybrid hyrax	6.43	1.56	8.34 b	1.63	1.91 b	.98	1.60	.000*
	MSE	7.76	2.16	8.72 b	2.37	.96 b	.51	0.90	.000*
	P value bet. groups	.191ns		.003*		.000*			
Left.1 st premolar inclination	Butterfly hyrax	7.37	2.39	12.46 a	3.48	5.09 a	5.09	5.80	.003*
	Hybrid hyrax	6.57	1.60	8.63 b	1.51	2.06 b	2.06	2.20	.000*
	MSE	7.61	2.17	8.41 b	2.08	.80 c	.80	0.70	.000*
	P value bet. groups	.355ns		.000*		.000*			

Significance level p≤0.05, \*significant, ns=non-significant

Post hoc test: Within the same comparison, means sharing the same superscript letter are not significantly different

Table (3) Descriptive statistics and comparison between (ANOVA test) and within group (i.e. between pre and post value) (paired t test) regarding arch depth; incisor inclination

GROUP	Pre		Post		Amount of change (post-pre)			P Within group	
	Mean	Std. Dev	Mean	Std. Dev	Mean	Std. Dev	Median		
Arch depth	Butterfly hyrax	26.92	2.87	26.19 a	2.47	-.74 a	.38	-.70	.000*
	Hybrid hyrax	25.93	2.47	25.39 a	2.43	-.53 a	.22	-0.50	.000*
	MSE	24.72	2.25	23.38 b	2.41	-	.60	-1.30	.000*
	P value bet. groups	.064ns		.007*		.000*			
Incisor inclination	Butterfly hyrax	117.31	3.65	114.46	3.37	-	2.00	-2.80	.000*
	Hybrid hyrax	118.45	4.29	114.67	4.30	-3.79 a	1.80	-3.70	.000*
	MSE	120.05	5.32	114.63	5.79	-	1.48	-5.30	.000*
		.243 ns		.992 ns		.001*			
Anterior suture opening	Butterfly hyrax	.09	.27	3.57 b	.47	3.47 b	.34	3.50	.004*
	Hybrid hyrax	.27	.44	3.93 b	.64	3.67 b	.36	3.70	.000*
	MSE	.30	.42	5.99 a	.46	5.69 a	.33	5.70	.002*
	P value bet. groups	.290 ns		.000*		.000*			
Posterior suture opening	Butterfly hyrax	.00	.00	2.14 c	.44	2.14 c	.44	2.20	.000*
	Hybrid hyrax	.00	.00	3.06 b	.37	3.06 b	.37	3.10	.000*
	MSE	.00	.00	5.16 a	.49	5.16 a	.49	5.05	.000*
	P value bet. groups	---		.000*		.000*			

Significance level p≤0.05, \*significant, ns=non-significant

Post hoc test: Within the same comparison, means sharing the same superscript letter are not significantly different

[figure not shown]

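### For posterior suture opening the SAP text ranks Hybrid significantly lowest, while the table it cites ranks Butterfly lowest and Hybrid significantly higher than Butterfly

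*SAP*

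**What the plan says.** The SAP file contains results as well as methods. In its outcomes section, under the comparison between Hybrid and conventional hyrax groups, the posterior suture item says that all arms started at zero. It then says of the post-treatment mean that the value "recorded in MSE was significantly higher than that recorded in Butterfly hydrax, while Hybrid hyrax recorded a significantly lower value" than the other two. The same ranking is repeated for the amount of change, again ending "while Hybrid hyrax recorded a significantly lower value than the other 2 groups". Both statements refer the reader to Table 3.

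That is the outcome Table 3, not the malocclusion table that carries the same number. Its posterior suture rows, identical for post value and change, are:

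| Arm | Mean | SD | Median change | Letter |
|---|---|---|---|---|
| Butterfly | 2.14 | 0.44 | 2.20 | c |
| Hybrid | 3.06 | 0.37 | 3.10 | b |
| MSE | 5.16 | 0.49 | 5.05 | a |

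The footnote explains that "means sharing the same superscript letter are not significantly different", so three different letters mean that all three arms differ.

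For change in hard palate maxillary width 6, the text gives Butterfly 3.37 (SD 0.96) and Hybrid 3.17 (SD 1.54). The outcome Table 2 gives Butterfly 3.17 (SD 1.54) and Hybrid 3.37 (SD 0.96).

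**The concern.** The protocol's aim is to compare the three expanders, and the results section concerned is headed as the Hybrid versus conventional comparison. On posterior suture opening, text and table agree that MSE is highest and that all three arms differ. They disagree on which of the other two arms is lowest.

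A reader of the text would conclude that the hybrid appliance opens the posterior suture significantly less than the conventional one. A reader of the table would conclude that it opens it significantly more. Anyone who carries the narrative into a report or a review would carry the first version. By the legible letters, this is one of only two measures that separate all three arms on post values (with nasal floor at the premolar), and one of four that do so on change. The contrast is therefore one that readers are likely to use.

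The width 6 exchange involves the same two arms and suggests that their labels were mixed up when the text was written.

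**Working it through.** **Inputs.** Means, SDs and letters come from the SAP's outcome Tables 2 and 3. Group sizes of 15, 15 and 16 (Butterfly, Hybrid, MSE) come from its demographic tables; the outcome tables state no n, so the same sizes are assumed. The SAP specifies that group comparisons were "performed by ANOVA test followed by Bonferroni post hoc test whenever a significance difference was detected". It defines change as the value after minus the value before.

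**1. Reproduce the stated p-values.** One-way ANOVA can be rebuilt from means and SDs.

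- Posterior suture, within-group sum of squares: 14×0.44² + 14×0.37² + 15×0.49² = 2.710 + 1.917 + 3.602 = 8.229. The mean square is 8.229/43 = 0.1914.
- Overall mean: (15×2.14 + 15×3.06 + 16×5.16)/46 = 3.490. The between-group mean square is 37.37.
- F(2,43) = 37.37/0.1914 = 195.3, p = 2.7e-22. The table states .000.
- The same method gives p = 0.189 for age (stated .190), 0.081 for width 6 pre (stated .083) and 0.022 for width 6 post (stated .023). The assumed group sizes and the tabled figures are consistent.

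**2. Size and direction of the contrast in Table 3.**

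- Hybrid minus Butterfly = 3.06 − 2.14 = +0.92, and 0.92/2.14 = 43%.
- SE = √(0.1914 × 2/15) = 0.160; t = 0.92/0.160 = 5.76 on 43 df; 95% CI 0.60 to 1.24; Bonferroni p = 2.5e-6.
- A plain two-arm t-test agrees: pooled SD = √[(0.44² + 0.37²)/2] = 0.407, SE = 0.148, t = 6.2, p about 1e-6.
- MSE minus Hybrid = +2.10 and MSE minus Butterfly = +3.02, both with Bonferroni p below 1e-15.

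The table's order is MSE > Hybrid > Butterfly. The text's order is MSE > Butterfly > Hybrid.

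**3. Width 6, where arithmetic can decide.** Post minus pre from Table 2:

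- Butterfly: 63.59 − 60.43 = 3.16 (table 3.17, text 3.37).
- Hybrid: 62.04 − 58.67 = 3.37 (table 3.37, text 3.17).

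The table is right to rounding, and the text has the two mean and SD pairs exchanged. The Hybrid–Butterfly difference is 0.20 (95% CI −0.66 to 1.06, Bonferroni p = 1.0) and both arms carry letter b, so only the order changes.

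**4. Which version of posterior suture opening is likelier?** Exchanging the Butterfly and Hybrid rows leaves F unchanged, because both arms have 15 patients. The stated p-value therefore cannot decide. Other evidence favours the table:

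- Hybrid molar distance change is 7.24 in the text and 7.42 in Table 1; 52.21 − 44.79 = 7.42 supports the table.
- The text calls the MSE change in molar inclination significantly higher than in the other arms. Table 2 shows MSE lowest on the right side, 2.08 against 5.66 and 4.85. Post minus pre gives 22.82 − 20.74 = 2.08, 24.24 − 18.58 = 5.66 and 23.27 − 18.43 = 4.84, which again supports the table.
- On every other nasal floor, hard palate and suture row, the tabled Hybrid change exceeds Butterfly: 2.60 v 2.20, 3.43 v 2.47, 3.37 v 3.17, 5.09 v 4.51 and 3.67 v 3.47. Table 3's posterior suture order fits this pattern; the text does not.

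**The case against.** The strongest objection is that the direction is not proven. Every pre-treatment value is 0.00, so post minus pre cannot test the row labels as it can for width 6. The file holds summary tables rather than patient data. The tables also have errors of their own: for left premolar inclination in Table 2, the change SDs repeat the means (5.09, 2.06 and 0.80). This stands. The documents prove a contradiction and make the text the likelier error, but no more than that.

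It can also be said that this is a slip in narrative, not in design or method, that the sentence cites the table where a reader can see the ranking, and that neither document draws a conclusion from it. That is fair on likely harm. It does not make the slip clerical, because a significant contrast between two randomised arms is stated twice in a direction that the cited table contradicts, and nothing elsewhere corrects it.

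Lesser points also stand. Neither document names a single primary variable, so posterior suture opening is one of 18 tabled measures with no stated priority. The SAP says "Difference data were non-parametric and were compared between groups using Kruskal Wallis test"; that test needs patient data, so the parametric figures above approximate the planned analysis of change. The width 6 exchange alters no significance statement and is supporting evidence only.

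**Conclusion.** The concern holds. For posterior suture opening, the SAP text and its own Table 3 give opposite, significant answers on Hybrid versus Butterfly. Taking the table as it stands, Hybrid exceeds Butterfly by 0.92 (43%; 95% CI 0.60 to 1.24; Bonferroni p = 2.5e-6), where the text reports Hybrid as significantly lower. For change in hard palate width 6, the text is shown to be wrong by the table's own pre and post means, but the 0.20 difference is not significant in either order.

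This rests on three assumptions: the outcome tables use 15, 15 and 16 patients; Butterfly is the protocol's conventional hyrax, as the SAP heading implies; and the Table 3 rows are labelled correctly, which is probable but unverified. The rows state no unit, so none is given here. The contradiction itself depends on none of these assumptions. It must be resolved before either version is used.

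**What to change.** Check the posterior suture opening and hard palate width 6 rows against the patient-level data, including the arm labels. If the tables are confirmed:

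- Rewrite both posterior suture statements (post value and change) to say that MSE was significantly higher than Hybrid, and Hybrid significantly higher than Butterfly.
- Exchange the Butterfly and Hybrid mean and SD pairs in the text on width 6 change.
- Base any conclusion about suture opening on the confirmed ranking.

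If the source data show that Table 3's labels are swapped, correct the table instead and keep the text. The left premolar inclination SDs, Hybrid molar distance change and the molar inclination wording can be checked at the same time. The cost is one source-data check and a few corrected sentences or rows. No new data or redesign is needed.

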## II-Comparison between pre and post values Hybrid and conventional hydrax groups

Comparing the pre and post values revealed that the post treatment value was significantly higher in post value compared to the pre value in molar and premolar distance (Fig.1), right and left molar rotation (Fig.2), right and left premolar rotation (Fig.3), nasal floor first premolar and molar (Fig.4), hard palate maxillary width first molar and premolar (Fig.5), right and left molar inclination (Fig.6), right and left premolar inclination (Fig.7) and anterior and posterior suture opening (Fig.10). On the other hand, Arch depth and incisor inclination recorded significantly lower post value compared to the pre value (Fig. 8,9), (Table 1-3)

Table (1) Descriptive statistics and comparison between (ANOVA test) and within group (i.e. between pre and post value) (paired t test) regarding molar and premolar distance; molar and premolar rotation right and left

GROUP	Pre		Post		Amount of change (post-pre)			P Within group	
	Mean	Std. Dev	Mean	Std. Dev	Mean	Std. Dev	Median		
Molar distance	Butterfly hyrax	43.55	1.97	49.43 b	2.41	5.88 c	1.39	5.77	.000*
	Hybrid hyrax	44.79	4.27	52.21 a	2.59	7.42 b	1.77	7.50	.000*
	MSE	42.14	3.25	51.01 ab	2.56	8.88 a	1.58	8.95	.000*
	P value bet. groups	.094ns		.016*		.000*			
Premolar distance	Butterfly hyrax	36.99	4.60	43.67 a	2.55	6.68 a	1.83	6.20	.004*
	Hybrid hyrax	36.65	3.15	42.73 a	2.70	6.08 a	1.84	5.90	.002*
	MSE	34.03	3.12	38.46 b	2.61	4.43 b	1.82	4.85	.002*
	P value bet. groups	.058 ns		.000*		.005*			
Molar rotation right	Butterfly hyrax	58.32	4.68	59.57	4.74	1.25	.67	1.10	.000*
	Hybrid hyrax	61.50	4.54	62.54	4.42	1.04	.58	1.10	.000*
	MSE	61.95	7.38	62.99	7.26	1.04	.65	0.90	.000*
	P value bet. groups	.175ns		.207 ns		.503 ns			
Molar rotation left	Butterfly hyrax	59.75	5.31	61.17	5.27	1.42	.51	1.50	.000*
	Hybrid hyrax	64.31	5.57	65.55	5.46	1.25	.82	1.10	.000*
	MSE	60.43	5.65	61.90	5.54	1.48	1.06	1.20	.000*
	P value bet. groups	.060 ns		.070 ns		.757 ns			
Premolar rotation right	Butterfly hyrax	74.71	6.68	75.84	6.64	1.13	.40	1.10	.000*
	Hybrid hyrax	73.79	6.58	74.71	6.48	.93	.48	0.90	.000*
	MSE	76.43	7.60	77.21	7.60	.78	.42	0.75	.000*
	P value bet. groups	.566 ns		.609 ns		.084ns			
Premolar rotation left	Butterfly hyrax	74.23	6.40	75.27	6.33	1.05	.32	1.10	.000*
	Hybrid hyrax	76.99	6.07	78.65	5.55	1.65	2.50	1.10	.000*
	MSE	75.14	5.83	76.16	5.95	1.02	.47	1.10	.000*
	P value bet. groups	.455ns		.283ns		.410ns			

Significance level p≤0.05, \*significant, ns=non-significant

Post hoc test: Within the same comparison, means sharing the same superscript letter are not significantly different

Table (2) Descriptive statistics and comparison between (ANOVA test) and within group (i.e. between pre and post value) (paired t test) regarding nasal floor, hard palate maxillary width molar and premolar; molar and premolar inclination right and left

GROUP	Pre		Post		Amount of change (post-pre)			P Within group	
	Mean	Std. Dev	Mean	Std. Dev	Mean	Std. Dev	Median		
Nasal floor 1 st .molar	Butterfly hyrax	65.13	5.07	67.33	1.67	2.20 b	1.49	1.80	.003*
	Hybrid hyrax	63.48	3.13	66.08	2.80	2.60 b	1.04	2.40	.000*
	MSE	62.00	3.36	66.38	3.07	4.38 a	.85	4.45	.000*
	P value bet. groups	.058ns		.397ns		.000*			
Nasal floor 1 st .premolar	Butterfly hyrax	34.57	1.55	37.04 c	1.17	2.47 c	1.02	2.40	.001*
	Hybrid hyrax	35.21	2.09	38.63 b	1.77	3.43 b	.74	3.50	.000*
	MSE	34.86	2.40	39.73 a	2.27	4.87 a	.62	5.00	.000*
		.701ns		.001*		.000*			
Hard palate Maxillary width 6	Butterfly hyrax	60.43	2.49	63.59 ab	2.15	3.17 b	1.54	3.10	.000*
	Hybrid hyrax	58.67	2.99	62.04 b	2.68	3.37 b	.96	3.40	.000*
	MSE	58.39	2.44	64.31 a	1.80	5.91 a	.92	6.10	.000*
	P value bet. groups	.083ns		.023*		.000*			
Hard palate Maxillary width 4	Butterfly hyrax	33.66	1.85	38.17 b	1.76	4.51 b	1.28	4.50	.001*
	Hybrid hyrax	34.22	1.79	39.31 ab	1.39	5.09 b	1.16	4.90	.001*
	MSE	33.99	1.58	40.34 a	1.56	6.35 a	1.25	6.10	.003*
	P value bet. groups	.677ns		.002*		.001*			
Right.1 st molar inclination	Butterfly hyrax	18.58	4.41	24.24	5.32	5.66 a	1.52	5.80	.000*
	Hybrid hyrax	18.43	5.33	23.27	5.20	4.85 a	2.10	6.00	.000*
	MSE	20.74	5.06	22.82	4.77	2.08 b	1.30	1.70	.000*
	P value bet. groups	.353ns		.734ns		.000*			
Left.1 st molar inclination	Butterfly hyrax	18.45	4.34	23.67	6.07	5.21 a	2.74	6.30	.000*
	Hybrid hyrax	19.09	3.08	23.71	3.68	4.62 a	1.62	4.90	.000*
	MSE	20.49	3.78	23.01	3.53	2.52 b	1.31	2.35	.000*
	P value bet. groups	.312ns		.892ns		.003*			
Right.1 st premolar inclination	Butterfly hyrax	6.70	2.51	11.72 a	3.96	5.02 a	2.18	5.90	.000*
	Hybrid hyrax	6.43	1.56	8.34 b	1.63	1.91 b	.98	1.60	.000*
	MSE	7.76	2.16	8.72 b	2.37	.96 b	.51	0.90	.000*
	P value bet. groups	.191ns		.003*		.000*			
Left.1 st premolar inclination	Butterfly hyrax	7.37	2.39	12.46 a	3.48	5.09 a	5.09	5.80	.003*
	Hybrid hyrax	6.57	1.60	8.63 b	1.51	2.06 b	2.06	2.20	.000*
	MSE	7.61	2.17	8.41 b	2.08	.80 c	.80	0.70	.000*
	P value bet. groups	.355ns		.000*		.000*			

Significance level p≤0.05, \*significant, ns=non-significant

Post hoc test: Within the same comparison, means sharing the same superscript letter are not significantly different

Table (3) Descriptive statistics and comparison between (ANOVA test) and within group (i.e. between pre and post value) (paired t test) regarding arch depth; incisor inclination

GROUP	Pre		Post		Amount of change (post-pre)			P Within group	
	Mean	Std. Dev	Mean	Std. Dev	Mean	Std. Dev	Median		
Arch depth	Butterfly hyrax	26.92	2.87	26.19 a	2.47	-.74 a	.38	-.70	.000*
	Hybrid hyrax	25.93	2.47	25.39 a	2.43	-.53 a	.22	-0.50	.000*
	MSE	24.72	2.25	23.38 b	2.41	-	.60	-1.30	.000*
	P value bet. groups	.064ns		.007*		.000*			
Incisor inclination	Butterfly hyrax	117.31	3.65	114.46	3.37	-	2.00	-2.80	.000*
	Hybrid hyrax	118.45	4.29	114.67	4.30	-3.79 a	1.80	-3.70	.000*
	MSE	120.05	5.32	114.63	5.79	-	1.48	-5.30	.000*
		.243 ns		.992 ns		.001*			
Anterior suture opening	Butterfly hyrax	.09	.27	3.57 b	.47	3.47 b	.34	3.50	.004*
	Hybrid hyrax	.27	.44	3.93 b	.64	3.67 b	.36	3.70	.000*
	MSE	.30	.42	5.99 a	.46	5.69 a	.33	5.70	.002*
	P value bet. groups	.290 ns		.000*		.000*			
Posterior suture opening	Butterfly hyrax	.00	.00	2.14 c	.44	2.14 c	.44	2.20	.000*
	Hybrid hyrax	.00	.00	3.06 b	.37	3.06 b	.37	3.10	.000*
	MSE	.00	.00	5.16 a	.49	5.16 a	.49	5.05	.000*
	P value bet. groups	---		.000*		.000*			

Significance level p≤0.05, \*significant, ns=non-significant

Post hoc test: Within the same comparison, means sharing the same superscript letter are not significantly different

[figure not shown]

Fig. (1) Bar chart illustrating mean value of molar and premolar distances in different groups

[figure not shown]

Fig. (2) Bar chart illustrating mean value of molar rotation in different groups

[figure not shown]

Fig. (3) Bar chart illustrating mean value of premolar rotation in different groups

[figure not shown]

Fig. (4) Bar chart illustrating mean value of nasal floor first molar and premolar in different groups

[figure not shown]

Fig. (5) Bar chart illustrating mean value of hard palate maxillary width first molar and premolar in different groups

[figure not shown]

Fig. (6) Bar chart illustrating mean value of molar inclination in different groups

[figure not shown]

Fig. (7) Bar chart illustrating mean value of premolar inclination in different groups

[figure not shown]

Fig. (8) Bar chart illustrating mean value of arch depth in different groups

[figure not shown]

Fig. (9) Bar chart illustrating mean value of incisor inclination in different groups

[figure not shown]

Fig. (10) Bar chart illustrating mean value of anterior and posterior suture opening in different groups

[figure not shown]

Fig. (11) Box plot illustrating value of difference in molar and premolar distance in different groups

[figure not shown]

Fig. (12) Box plot illustrating value of difference in molar and premolar rotation in different groups

[figure not shown]

Fig. (13) Box plot illustrating value of difference in nasal floor difference in different groups

[figure not shown]

Fig. (14) Box plot illustrating value of difference in hard palate maxillary molar and premolar in different groups

[figure not shown]

Fig. (15) Box plot illustrating value of difference in molar and premolar inclination in different groups

[figure not shown]

Fig. (16) Box plot illustrating value of difference in arch depth in different groups

[figure not shown]

Fig. (17) Box plot illustrating value of difference in incisor inclination in different groups

[figure not shown]

Fig. (18) Box plot illustrating value of difference in anterior and posterior suture opening in different groups

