So the aim of this study was to evaluate the effect of three types of rapid maxillary expanders (conventional, Hybrid and MSE) using cone beam computed tomography (CBCT)

Aim of study

The aim of this study was to compare the effect of three types of rapid maxillary expanders (conventional, Hybrid and MSE) using cone beam computed tomography (CBCT)

The secondary outcomes

- a- Evaluation of periodontal condition of maxillary first permanent molars, both clinically and radiographically using CBCT
- b- Evaluation of Airway.

Material and Methods

Study design:

Prospective randomized controlled trial

Study setting and population:

This study will be conducted on patients seeking orthodontic treatment in the outpatient clinic, Orthodontic department, Faculty of Dental Medicine, Al-Azhar University, Cairo, Boys branch.

Eligibility criteria of population:

The patients will be selected according to the following inclusions criteria:

- 1- Patients suffering maxillary collapse with a skeletal background
- 2- Patients with unilateral or bilateral posterior crossbite.
- 3- Patients with reduced or average anterior face height.
- 4- Patients with no periodontal disease.
- 5- Patients with good oral hygiene and general health.
- 6- No systemic diseases that may affect bone quality or interfere with orthodontic treatment.
- 7- Patients with erupted maxillary permanent first molars and premolars.
- 8- Patients with no previous orthodontic treatment.

Sample size:

Sample size calculation using G power software was based on the observed effect sizes derived from previous article. ⁽²⁰⁾

The calculation indicated that for a study with a power of 0.95 and an alpha of 0.05, a total of at least 45 patients (15 patients in each group) .

Group allocation:

The patients will be classified and randomly allocated into three equal groups, using online generated randomization plan (Graph Pad) found at the website

<http://www.graphpad.com/quickcalcs/index.cfm>:

- Group (1): The conventional hyrax.
- Group (2): The Hybrid hyrax.
- Group (3): The MSE expander.

Interventions:

The current study was conducted on a total sample of forty five young adult orthodontic patients presented with transverse maxillary deficiency with an age ranged from 11-16 years.

- All patients in this study will undergo a special protocol for oral hygiene measures for one month to standardize as possible the oral hygiene measure before expansion.

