## Results

### I-Demographic data

**Age:** Patients age ranged from 11.7 to 15.8 years. There was no significant difference in age between groups ( $p=0.19$ ), (Table 1, Fig.1)

**Cross bite:** In Butterfly hyrax, 73.3% of cases were bilateral, in comparison to 53.3% and 56.3% bilateral cases in Hybrid hyrax and MSE respectively; with no significant difference between groups ( $p=0.477$ ), (Table 2, Fig.2)

**Malocclusion:** In Butterfly hyrax and Hybrid hyrax, 73.3% of cases were class 3, in comparison to 75% class 3 cases in MSE; with no significant difference between groups ( $p=0.993$ ), (Table 3, Fig.3)

Table (1) Descriptive statistics and comparison between age between groups (ANOVA test)

	Mean	Std. Dev.	Min	Max	P value
Butterfly hyrax	14.50	1.04	11.70	15.80	0.190 ns
Hybrid hyrax	13.96	1.21	11.70	15.40	
MSE	13.81	.98	12.10	15.10	

Significance level  $p \leq 0.05$ , ns=non-significant

Table (2) Distribution of cases according to cross bite and comparison between age between groups (Chi square test)

CROSS_BITE	Groups			P value
	Butterfly hyrax	Hybrid hyrax	MSE	
Unilateral	4 (26.7%)	7 (46.7%)	7 (43.8%)	0.477 ns
Bilateral	11 (73.3%)	8 (53.3%)	9 (56.3%)	
Total	15	15	16	

Significance level  $p \leq 0.05$ , ns=non-significant

Table (3) Distribution of cases according to cross bite and comparison between age between groups (Chi square test)

MALOCCLUSION	Groups			P value
	Butterfly hyrax	Hybrid hyrax	MSE	
Class 1	4 (26.7%)	4 (26.7%)	4 (25%)	0.993 ns
Class 3	11 (73.3%)	11 (73.3%)	12 (75%)	
Total	15	15	16	

Significance level  $p \leq 0.05$ , ns=non-significant

[figure not shown]

Fig. (1) Bar chart illustrating mean age in different groups

[figure not shown]

Fig. (2) Bar chart illustrating distribution of unilateral and bilateral cases in different groups

[figure not shown]

Fig. (3) Bar chart illustrating distribution of malocclusion classes in different groups

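### Rotation and inclination change are each tested twice, on anatomical right and left, with no objective about side, no record of the crossbite side and no rule for combining the two results

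*SAP*

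**What the plan says.** The protocol's eligibility criteria admit "Patients with unilateral or bilateral posterior crossbite". The SAP's demographic section reports that in the Butterfly arm "73.3% of cases were bilateral, in comparison to 53.3% and 56.3% bilateral cases in Hybrid hyrax and MSE respectively". The counts in its crossbite table are 4 of 15, 7 of 15 and 7 of 16 unilateral.

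Outcome Table 1 covers results "regarding molar and premolar distance; molar and premolar rotation right and left", and outcome Table 2 covers "molar and premolar inclination right and left". Each side has its own row, its own between-group p-value and, where significant, its own post hoc letters.

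The SAP's Statistical analysis section says: "Difference data were non-parametric and were compared between groups using Kruskal Wallis test". It gives no rule for side: none for choosing one, averaging the two, or allowing for both coming from the same patient. The protocol's aim and secondary outcomes do not mention side.

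**The concern.** None of the three appliances is described as acting on one side, so separate right and left tests answer no stated question. In a unilateral patient the right may be the crossbite side or the other one, and the documents do not say which. A right or left row therefore describes no defined set of teeth in those patients.

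Three things are at stake:

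- **Precision.** Each test uses one side's data where two measurements per patient exist.
- **Multiplicity.** Each measure has two correlated chances of a significant result.
- **Interpretation.** If the two sides differ, nothing says which result counts. This arises once, for premolar inclination change.

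**Working it through.** **1. Crossbite counts.** Unilateral: 4 + 7 + 7 = 18 of 46 (39.1%). Bilateral: 11 + 8 + 9 = 28. Pearson chi-square on the 2 x 3 table is 1.479 on 2 df, p = 0.477, which reproduces the SAP's figure. If each unilateral patient is assumed to have one side out of crossbite, those sides make up 4/30 = 13.3% (Butterfly), 7/30 = 23.3% (Hybrid) and 7/32 = 21.9% (MSE).

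**2. Do the sides disagree overall?** Printed between-group p-values for change:

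| Measure | Right | Left | Verdict at 0.05 |
|---|---|---|---|
| Molar rotation | .503 | .757 | ns on both |
| Premolar rotation | .084 | .410 | ns on both |
| Molar inclination | .000 | .003 | significant on both, letters a, a, b on both |
| Premolar inclination | .000 | .000 | significant on both |

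The verdicts agree in 4 of 4 pairs.

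**3. The one discrepancy.** Premolar inclination change, outcome Table 2 (Butterfly, Hybrid, MSE):

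- Right: 5.02 a, 1.91 b, 0.96 b. Hybrid minus MSE = 0.95.
- Left: 5.09 a, 2.06 b, 0.80 c. Hybrid minus MSE = 1.26.

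The premolar inclination item in the SAP's Outcomes section says MSE differs significantly from both other arms, on both sides. The right-side letters contradict this for Hybrid. The item also calls the MSE change higher, whereas the table shows it lowest.

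The left row's SD column reads 5.09, 2.06 and 0.80, the same as its means. For Butterfly, the pre-post correlation implied by the printed SDs is (SDpre² + SDpost² - SDchange²) / (2 x SDpre x SDpost):

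- Left: (2.39² + 3.48² - 5.09²) / (2 x 2.39 x 3.48) = -8.09 / 16.63 = -0.49.
- Right: (2.51² + 3.96² - 2.18²) / (2 x 2.51 x 3.96) = 17.23 / 19.88 = 0.87.

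The left value is implausible beside the right, so the column looks like a copying error.

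The SAP's rank test cannot be rerun from summaries. Using one-way ANOVA with pooled variance, 43 df and Bonferroni x 3 as an approximation, Hybrid against MSE gives:

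- Right: pooled variance 1.951, SE = sqrt(1.951 x (1/15 + 1/16)) = 0.502, t = 0.95/0.502 = 1.89, adjusted p = 0.196.
- Left, SDs as printed: adjusted p = 0.824, so letter c is not reproduced.
- Left, right-side SDs assumed: t = 1.26/0.502 = 2.51, adjusted p = 0.048.

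An unequal-variance t test with the same x 3 correction gives 0.009 on the right, so even the shared letter there depends on the post hoc method.

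**4. Do the two contrasts differ from each other?** Gap = 1.26 - 0.95 = 0.31. Its variance is the sum, over the two arms, of (sR² + sL² - 2·rho·sR·sL)/n. For assumed rho of 0, 0.5 and 0.8, and either choice of left SDs, p runs from 0.08 to 0.63.

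**5. Multiplicity.** Two tests per measure at 0.05: 1 - 0.95² = 9.75% if independent, and less if positively correlated.

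**6. Precision.** With equal side SDs, the variance of the two-side mean relative to one side is (1 + r)/2. At r = 0.3 the SE ratio is sqrt(0.65) = 0.81, and at r = 0.7 it is sqrt(0.85) = 0.92. That is an SE 19% to 8% smaller.

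With unequal SDs, the SD of the mean is sqrt((sR² + sL² + 2·r·sR·sL)/4). For the same r of 0.3 to 0.7:

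| Row | SD right / left | SD of two-side mean | Average of the two SDs |
|---|---|---|---|
| Hybrid premolar rotation | 0.48 / 2.50 | 1.34 to 1.43 | 1.49 |
| Butterfly molar inclination | 1.52 / 2.74 | 1.76 to 1.98 | 2.13 |
| MSE molar rotation | 0.65 / 1.06 | 0.70 to 0.79 | 0.86 |

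The mean beats the average side in each row, but not the less variable side.

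**The case against.** The strongest defence is that reporting paired teeth by side is transparent and changed no overall conclusion. That stands. A reader might infer from the premolar letters that the two sides conflict. The documents do not support this: the contrasts have the same direction, the gap between them is compatible with chance, and the left row is visibly defective. A significant result on one side beside a non-significant one on the other is not a conflict, and nothing links the letter to crossbite side.

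A reader might also infer that mixing crossbite and non-crossbite teeth biases the comparison of arms. No bias is shown. Allocation was random and crossbite type does not differ significantly between arms (p = 0.477, though with little power). Calling the second side unaffected is an assumption, since all patients were selected for a skeletal maxillary deficiency.

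It is also fair to say that a two-side mean still pools crossbite and non-crossbite teeth. It removes the arbitrary choice of side and makes each unilateral patient contribute both sides, but it does not separate them. Finally, the protocol does not list rotation or inclination among its named secondary outcomes, which limits the weight of the point.

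**Conclusion.** The point holds as one of efficiency and clarity. Four measures are tested eight times on a split that no objective calls for, with the crossbite side unidentified in 18 of 46 patients and no rule for combining two correlated results. All four overall verdicts agree between sides.

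The familywise figure of 9.75% per measure assumes independent tests. The 8% to 19% gain in standard error assumes equal side SDs and a between-side correlation of 0.3 to 0.7, which the documents do not give. It concerns means, whereas the SAP tests change by ranks. The result after averaging needs patient-level data, so no corrected p-value can be given.

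The Hybrid against MSE result for premolar inclination change is unresolved until the left row is checked.

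**What to change.** 1. For molar and premolar rotation and inclination, compare groups on each patient's mean of right and left change, with the SAP's own test for change and a named post hoc procedure. This gives four tests in place of eight.
2. Keep the right and left rows as description, without p-values.
3. If the crossbite side was recorded, list change by crossbite and non-crossbite side, descriptively, for the 18 unilateral patients. The documents do not show that it was recorded.
4. Check the SD column of the left premolar inclination change row against the data. Then reconcile the premolar inclination text with outcome Table 2, both on whether MSE differs from Hybrid and on the direction of the difference.

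The cost is four re-run comparisons on values already measured. The downside is that side-specific p-values are no longer reported, and where one side is much less variable the mean may be less precise than that side alone.
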